6.5 Exclusion criteria

The following criteria will be checked at the time of study entry (i.e. following screening, at the time that participants are enrolled into the vaccine trial itself). If any apply at the time of study entry, the subject must not be included in the study:

- Previous vaccination with an investigational malaria vaccine or with any rabies vaccine.
- Use of any investigational or non-registered drug or vaccine other than the study vaccine(s) within 30 days preceding the first dose of study vaccine, or planned use up to 30 days after the third dose.
- Chronic administration (defined as more than 14 days) of immuno-suppressants or other immune-modifying drugs within six months prior to the first vaccine dose. This will include oral steroids and inhaled steroids, but not topical steroids.
- Planned administration/administration of a vaccine not foreseen by the study protocol within 30 days before the first dose of study vaccine(s) with the exception of tetanus toxoid.
- Previous vaccination with a vaccine containing MPL and/or QS-21 such as RTS,S.
- Any confirmed or suspected immunosuppressive or immunodeficient condition, including human immunodeficiency virus (HIV) infection.
- Any confirmed or suspected autoimmune disease
- History of allergic reactions or anaphylaxis to immunizations or to any vaccine component.
- History of serious allergic reactions to any substance, requiring hospitalization or emergent medical care
- History of allergy to tetracycline, doxycycline or neomycin
- History of splenectomy
- Serum ALT ≥35 IU/L
- Serum creatinine level >133 μ mol /L (1.5 mg/dL)
- Hb <11 g/dL for males and <10 g/dL for females
- WBC $<3.0 \times 10^3$ /mm³ or $>13.5 \times 10^3$ /mm³
- Absolute lymphocyte count $\leq 1.0 \ge 10^3 / \mu l$
- Thrombocytopenia < 100,000/µl
- More than trace protein, more than trace hemoglobin or positive glucose in urine

- Administration of immunoglobulins and/or any blood products within the three months preceding the first dose of study vaccine or planned administration during the study period.
- Suspected or known current alcohol or illicit drug abuse.
- Pregnancy or positive urine beta-HCG on the day of or prior to immunization.
- Breastfeeding
- Simultaneous participation in any other interventional clinical trial.

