7.1.5 Detailed description of study visits

Day -35 to -1 Screening /inclusion of participants

Meetings will be held with city administrative and medical authorities to explain the purpose of the study. These will be followed by meetings with the traditional authorities and the heads of families for village-level "permission to enter." Subsequently, general information about the study will be disseminated through the local radio station. Target population will be invited for screening as described in investigator's subject recruiting SOPs. Screening will be performed until 40 volunteers are included.

Visit 1 (may take place over more than one visit)

- Written informed consent for screening
- Assignment of participant ID number
- Medical history of participant
- Physical examination of all body major systems: Ear-Nose-Throat, Pulmonary, Cardiovascular, Musculoskeletal, Central Nervous, Renal, Gastro-intestinal and Skin. All findings will be recorded on screening forms.
- Collect 5-10 ml venous blood sample to measure:
 - Hematology: Complete Blood Count (CBC) which includes: red blood cells, platelets, white blood cell count, lymphocyte count, hemoglobin, mean corpuscular volume and mean corpuscular hemoglobin concentration.
 - Biochemistry: serum creatinine and ALT
- Beta-HCG pregnancy test on urine for females
- Collect urine: dipstick for blood, glucose and protein.
- Check of inclusion and exclusion criteria
- Prepare an ID card containing participant's unique study number and photo for enrolled participants.

Vaccination 1

Day 0: Visit 2

Before vaccination:

- Review screening laboratory test results
- Review inclusion/exclusion criteria and check of contraindications/precautions
- Written informed study consent for vaccination
- Randomization and assignment of randomization number
- Record any complaints, symptom-directed physical examination, and examination of the immunization arm(s) for any abnormalities.
- Record vital signs: oral temperature, blood pressure, pulse
- Record baseline data for solicited general symptoms
- Collect 5-10 ml venous blood sample to measure:
 - CBC, hemoglobin electrophoresis, creatinine, ALT
 - Serum for anti-MSP1 antibody titer (store at \leq -20°C)
- Collect urine for β-HCG test for females
- Confirm that the participant's study number agrees with the label on syringe.
- Administer study vaccine dose 1; record date and time of injection

After vaccination:

- Observe for a minimum of 30 minutes

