| Urine β-HCG | ● ^a | ● ^b | | | ● ^b | | | ● ^b | | | ٠ | ● ^d |
| CBC | ● ^a | ● ^c | | ٠ | • ^c | | ٠ | • ^c | | ٠ | ٠ | ● ^d |
| Serum chemistry (Creatinine, ALT) | ● ^a | •° | | ٠ | • ^c | | ٠ | • ^c | | ٠ | ٠ | ● ^d |
| Serum for anti-MSP1 response | | •° | | ٠ | •° | | ٠ | • ^c | | ٠ | ٠ | ● ^e |
| Monthly home visit by local guides | | | | | | | | | | | | • ^h |
| Review of health status | | | | | | | | | | | | ● ⁱ |
| Scheduled blood volume (ml) | 5-10 | 5- 10 | 0 | 5- 10 | 5- 10 | 0 | 5- 10 | 5- 10 | 0 | 5- 10 | 5- 10 | 15-30 |
| Cumulative Blood Volume (ml) | 5-10 | 10- 20 | 10- 20 | 15- 30 | 20- 40 | 20-40 | 25- 50 | 30- 60 | 30-60 | 35- 70 | 40- 80 | 55-110 |

a. Performed within 35 days prior to immunization

b. Performed just prior to each immunization

c. Blood collected just prior to each immunization

d. CBC, creatinine, ALT and urine β-HCG will be determined every 3 months from study Day 180 through study Day 364

e. Serum for MSP1 antibodies collected every 3 months from study Day 180 through study Day 364

f. Pre-dose and 30mn after each dose

g. Performed each time symptoms/signs evoking clinical malaria are present

h. Monthly local guides home visits to check the status of participants starting from study Day 120

i. Record any new onset chronic or acute diseases or other medically significant conditions, unscheduled clinic visits and any new treatments since previous scheduled study visit.

Table 2: Intervals between study visits

| Interval | Size of interval in days |
|---------------------------------|--------------------------|
| Visit $2 \rightarrow Visit 7$ | 14 ± 3 |
| Visit $2 \rightarrow Visit 8$ | 30 ± 7 |
| Visit $8 \rightarrow Visit 13$ | 14 ± 3 |
| Visit $8 \rightarrow Visit 14$ | 30 ± 7 |
| Visit $14 \rightarrow Visit 19$ | 14 ± 3 |
| Visit $14 \rightarrow Visit 20$ | 30 ± 7 |

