12.5.3 Analysis of safety

The overall percentage of participants with at least one local adverse event (solicited and unsolicited) and the percentage with at least one general adverse event (solicited and unsolicited) during the 8-day follow-up period after vaccination will be tabulated. The incidence, intensity and relationship of individual solicited symptoms over the 8-day follow-up period will be calculated per group and vaccine dose.

The number of participants with at least one report of an unsolicited adverse event, classified by WHO-preferred terms, reported up to 30 days after vaccination will be tabulated per group and vaccine dose. The intensity and relationship to vaccination of the unsolicited symptoms reported will also be assessed.

Serious adverse events are expected to be rare, but where observed will be described. Comparisons of incidence of symptoms, local and general symptoms will be made based on a two-tailed Fischer exact test. Analysis of safety during the 12-month follow-up period will consist of comparison of incidence of serious adverse events as well as hemoglobin, creatinine and ALT levels.

Clinical laboratory parameters

Hematological (CBC) and biochemical (ALT, creatinine) laboratory parameters will be measured at specific time points, Days 0, 14, 30, 44, 60, 74, 90 and starting on day 180 every 3 months. Clinically relevant abnormal values will be tabulated and a trend analysis could be performed if deemed necessary.

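### The stated 12-month comparison of laboratory levels covers only hemoglobin, creatinine and ALT; white cells, lymphocytes and platelets get an abnormal-value table and an optional trend analysis (minor)

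*Protocol*

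**What the plan says.** Section 12.5.3 defines the safety analysis for the 12-month follow-up: it "will consist of comparison of incidence of serious adverse events as well as hemoglobin, creatinine and ALT levels". Three laboratory variables are named.

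The data collected are wider. Section 7.1.5 describes the complete blood count (CBC) as one "which includes: red blood cells, platelets, white blood cell count, lymphocyte count, hemoglobin", among other items. Section 12.5.3 places the CBC, ALT and creatinine on Days 0, 14, 30, 44, 60, 74 and 90. Footnote d of the schedule of procedures adds that "CBC, creatinine, ALT and urine β-HCG will be determined every 3 months from study Day 180 through study Day 364".

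For the whole laboratory panel, 12.5.3 then provides: "Clinically relevant abnormal values will be tabulated and a trend analysis could be performed if deemed necessary". It does not say whether that table is by arm or which cut-offs apply.

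Section 6.5 sets entry limits for white cells, lymphocytes and platelets (for the last, "Thrombocytopenia < 100,000" per µl), as it does for hemoglobin, creatinine and ALT.

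**The concern.** All six variables serve as safety criteria at entry, but only three are named in the comparison of levels, and no reason is given. The wording reads as a closed list rather than as examples.

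Safety is the primary objective, and the test product contains two immunostimulants, so white-cell and lymphocyte counts are natural variables to set side by side by arm. Participants start inside the entry limits. A moderate fall or rise would leave most values in range, and a table restricted to clinically relevant abnormal values would show little of it. The data that could show it are already being collected.

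**Working it through.** **The plan's own figure.** The protocol states no power or effect size for laboratory values. Its nearest figure is Table 4 in section 12.4, the chance of at least one event among 20: 1 − (1 − p)^20. For p = 0.01, 0.05, 0.08 and 0.10 this gives 0.182, 0.642, 0.811 and 0.878, which agrees with the printed 0.18, 0.64, 0.81 and 0.88.

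**Inputs from the protocol**
- 40 adults randomised 1:1, so 20 per arm (6.1).
- Nine post-baseline CBCs: six from Day 14 to Day 90, plus visits 21 to 23.
- A two-tailed Fisher exact test, named for symptoms only (12.5.3). No test is named for laboratory levels.

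**Assumptions, not in the protocol**
- Normally distributed values and two-sided 5%.
- A value counts as abnormal beyond c = 2 SD or c = 1.645 SD on the side of the shift.
- Within-person correlation r of 0.5 to 0.9 across visits, equal for all pairs of visits.

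**One visit.** For levels I use a two-sample t-test with 38 degrees of freedom, critical value 2.024 and noncentrality d × √(20/2) = 3.162d, where d is the shift in SD. For abnormal counts, the proportion flagged is Φ(−c) in the control arm and Φ(−c + d) in the shifted arm, with exact Fisher power on 20 v 20.

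At d = 1:
- c = 2: 2.3% v 15.9%, or about 0.5 v 3.2 of 20.
- c = 1.645: 5.0% v 25.9%, or about 1.0 v 5.2 of 20.

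| Shift (SD) | Levels | Abnormal counts, c = 2 | Abnormal counts, c = 1.645 |
|---|---|---|---|
| 0.5 | 34% | 1% | 4% |
| 0.75 | 64% | 3% | 14% |
| 1.0 | 87% | 14% | 33% |
| 1.25 | 97% | 35% | 58% |

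With 18 per arm at 1 SD, levels give 83% and abnormal counts 12% to 27% (outer 2.5% and 5% tails).

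**A shift that persists over nine visits.** For levels, compare participant means. Their variance is r + (1 − r)/9, so r = 0.5, 0.7 and 0.9 give 0.556, 0.733 and 0.911. A 1 SD shift then equals 1.342, 1.168 and 1.048 SD of the mean. For counts, compare participants who are ever abnormal. That probability is 1 − E[(1 − Φ((d − c − √r·Z)/√(1 − r)))^9], with Z standard normal.

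| Shift (SD) | r | Levels | Ever abnormal, c = 2 | Ever abnormal, c = 1.645 |
|---|---|---|---|---|
| 1.0 | 0.5 | 98.5% | 71% | 74% |
| 1.0 | 0.7 | 95% | 56% | 66% |
| 1.0 | 0.9 | 90% | 39% | 52% |
| 0.75 | 0.5 | 87% | 40% | 48% |
| 0.75 | 0.7 | 77% | 29% | 39% |
| 0.75 | 0.9 | 68% | 17% | 27% |
| 0.5 | 0.5 | 54% | 16% | 21% |
| 0.5 | 0.7 | 44% | 11% | 16% |
| 0.5 | 0.9 | 37% | 5% | 11% |

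Repeated visits help both approaches. Levels stay ahead in every row. The useful gain lies at about 0.75 to 1.25 SD for a single-visit shift and at about 0.75 to 1 SD for a persistent one.

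**Other routes to a between-arm view**
- Laboratory changes can be adverse events (10.1.1), but 12.5.3 tabulates unsolicited events by group only to 30 days after each dose, that is to about Day 60 + 30 = Day 90. Section 10.1.3 limits recording to the defined time frames.
- The preliminary analysis in 12.6 treats safety by group, but it covers data after three doses and names no laboratory variable.
- The trend analysis has no trigger and is not stated to be by arm.

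None of these secures a comparison of the three counts through Day 364.

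**The case against.** A reader might infer that white cells, lymphocytes and platelets are never compared between arms, and that a real shift would usually be missed. The protocol supports neither statement. Abnormal CBC values are tabulated and nothing says that the table pools the arms. A trend analysis is allowed, and laboratory events can enter the by-group tables of unsolicited events. For a persistent 1 SD shift, counting participants who are ever abnormal has at least 50% power in five of the six settings above. At 0.5 SD or less the comparison of levels is weak too. There the cause is the sample size, and section 12.4 says openly that the trial is not powered for group differences.

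It can also be said that by-arm laboratory summaries belong in the Report and Analysis Plan named in 14.5.2 and 14.6, which is not shown. That would answer a protocol that was silent. Here the protocol states its own list, and the plan would have to go beyond it.

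Two further points have some force. ALT was the one event judged possibly or probably vaccine-related in the Gambian adult studies (4.3.1), and the earlier US studies reported no significant hematological abnormality, so the choice of variables is not arbitrary. The safety committee also reviews accumulating data before doses 2 and 3 (14.4). This lowers the severity, but it gives no between-arm comparison of these counts to the end of follow-up.

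Finally, a descriptive table has no power as such. The percentages above measure how much information each form of summary keeps; they do not propose a set of tests.

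**Conclusion.** The point holds in limited form. Section 12.5.3 restricts the stated 12-month comparison of levels to hemoglobin, creatinine and ALT. The other three counts have an abnormal-value table without stated grouping or cut-offs, and an optional trend analysis. A moderate within-range shift could be missed.

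At 1 SD, comparing levels detects 87% against 14% to 33% at a single visit, and about 90% to 99% against 39% to 74% when the shift persists. These figures depend on assumed normality, cut-offs, correlation and 20 evaluable participants per arm. No wrong figure is involved, and the severity is low.

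**What to change.** In section 12.5.3, extend the list of compared levels to hemoglobin, white cell count, lymphocyte count, platelets, creatinine and ALT. Summarise the added three by arm and visit, in the same descriptive way as the three already named.

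The cost is three more rows in a planned table, with no new samples or visits. The downside is three more descriptive comparisons without multiplicity control, so an isolated difference should be read with caution. Naming the variables before unblinding also avoids choosing them later under the optional trend analysis.

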12.6 Preliminary analysis

Safety, reactogenicity and immunogenicity data after three vaccine doses will be compiled by Statistics Collaborative Inc., Washington D.C. based on CRF data transcribed on site. Analysis of safety will be done for each group without revealing the assignment of individual participants.

12.7 Administrative matters

To comply with Good Clinical Practices important administrative obligations relating to investigator responsibilities, monitoring, archiving data, audits, confidentiality and publications must be fulfilled. See Appendices 16.4 and 16.5 for details.

13 TIME FRAME

Screening: June 2003 Dose 1: June 2003 Dose 2: July 2003 Dose 3: August 2003 Start Post-immunization Surveillance Period: October 2003 Preliminary Report: March 2003 Final Report: October 2004

14 ETHICAL CONSIDERATIONS

14.1 Statement of Compliance and Ethical Reviews

The study is under FDA IND BB-9202 and will be conducted according to current Good Clinical Practices, US 21 CFR Part 50-Protection of Human Subjects and Part 56-Institutional Review Boards, U.S. Army Regulation AR 40-38 and AR 70-25, and the applicable rules and regulations of Mali.

The FMPOS Ethical Review Committee will review and approve the protocol prior to study start. In addition to the review by the Human Subjects Research Review Board (HSRRB) of the Office of the Surgeon General, US Army, the study will be reviewed and approved by DMID and the NIAID and University of Maryland IRBs. Documentation of the approval by these ethical review boards will be conserved in the PI's study file.

14.1.1 Institutional Review Boards (IRB)

All amendments will be submitted to the FMPOS IRB (FWA00001769), the NIAID and UMB IRBs, the HSSRB and DMID. No amendments will go into effect without written approval from the FMPOS IRB, the NIAID IRB, the UMD IRB, HSRRB and DMID except when necessary to eliminate immediate hazards to the participants. Protocol deviations will also be reported to all the local IRBs and the HSRRB according to each IRB's policy. Also with regard to protocol violations, data will be entered and checked for missing or out-ofrange or other inaccurate information. Source documents will be examined to determine whether missing data were not transcribed, unavailable or missing for unknown reasons and this information will be coded and documented in the database.

The investigators will inform all the IRBs and DMID of the following:

- All subsequent protocol amendments, informed consent changes or revisions of other documents originally submitted for review
- Serious and/or unexpected adverse events occurring during the study, where required
- New information that may affect adversely the safety of the participants or the conduct of the study
- An annual update and/or request for re-approval, where required
- When the study has been completed, where required.

14.2 Informed consent

The principles of informed consent in the current edition of the Declaration of Helsinki will be implemented in each clinical study before any protocol-specified procedures or interventions are carried out.

Information will be given in both oral and written form whenever possible and deemed appropriate by the IRB.

The written consent documents will embody the elements of informed consent as described in the current edition of the Declaration of Helsinki, will adhere to the ICH Harmonized Tripartite Guideline for Good Clinical Practice and will also comply with applicable Malian regulations.

14.3 Role of Local Medical Monitor (Local Safety Monitor)

[name] is the Local Medical Monitor for this study. The term Local Medical Monitor is equivalent to the ICH term "Sponsor's Medical Expert". [name] *curriculum vitae* will be maintained on record. He is a qualified and experienced physician not otherwise associated with this protocol, who is able to provide medical care to research subjects for conditions that may arise during the conduct of the study, and who will monitor the subjects during the conduct of the study. The medical monitor is required to review all serious adverse events (per ICH definitions) associated with the protocol and provide an unbiased written report of the event within 10 calendar days of the initial report. At a minimum, the local medical monitor should comment on the outcomes of the serious adverse event (SAE) and relationship of the SAE to the test product. The medical monitor should also indicate whether he concurs with the details of the report provided by the study investigator.

The Local Medical Monitor will support the clinical investigators and act as a link between the investigators and the DSMB.

Version 19, DEAP/MRTC/MMVDU CONFIDENTIAL

The PI will report all serious adverse events to the Local Medical Monitor. He will review all serious adverse events associated with the protocol and will provide an unbiased written report of the event within 10 calendar days of the initial report. At a minimum, this report will comment on the outcomes of the adverse event and relationship to vaccination and indicate if the Local Medical Monitor concurs with the details of the report provided by the investigators.

> • The involvement of the Local Medical Monitor will be particularly important when decisions related to safety of participants have to be made quickly. Code break envelopes will be in his safekeeping and he may unblind individual study participants if deemed necessary for medical and/or ethical reasons. In exceptional circumstances, for example a death possibly related to vaccination, he would have the authority to suspend the whole or any specific aspect of the trial pending review by the SMC and DSMB.

The Medical Monitor may recommence the trial after discussions the DSMB and sponsors, if the DSMB recommends resuming the trial and the sponsors agree. Notification will then be made to all IRBs.

[name] will be on-site during active phases of immunization and during the immediate post-vaccination follow-up period. [name] [name], a medical staff member at the Bandiagara CSREF, will act as the on-site local Medical Monitor in support of [name] between the vaccinations. [name] is residing in Bandiagara full time, but is occasionally required to travel out of Bandiagara for professional duties, during which time, in consultation with [name] and the senior study investigators, he will designate another qualified physician on staff at CSREF and familiar with the study to cover his responsibilities.

The Local Medical Monitor's role will include:

- Acting as the study volunteers' advocate
- Promptly communicating relevant safety information to the SMC and DSMB
- Providing advice to the investigators on whether a set of clinical circumstances in a study warrants formal notification to the USAMMDA, the SMC and DSMB.
- Providing clinical advice on any illness in study subjects especially in circumstances in which treatment might influence the course of the trial.
- Review all SAEs as outlined above

The Local Medical Monitor will liaise closely with the PI throughout the course of the trial and relay relevant safety information to the PI, the SMC and the DSMB. The PI will inform the FMPOS IRB, the SMC and USAMMDA.

14.4 Safety Monitoring Committee (SMC)

An independent Safety Monitoring Committee will be constituted to help the Medical Monitor review safety data in real time. This committee will consist of the Local Medical Monitor and at least 2 other independent experts. The role of the SMC will be to review safety data between immunizations and to approve progression to the next immunization,

Version 19, DEAP/MRTC/MMVDU CONFIDENTIAL

whereas the role of the DSMB will be to assess and evaluate the accumulated safety and immunogenicity data from this trial and preceding trials, in order to make global decisions regarding the future of this vaccine formulation; the DSMB will not be required to meet during the conduct of this study. The Safety Monitoring Committee will hold two regularly scheduled conference calls, to review the safety data generated from the trial up to that point: the first will occur three weeks after the 1st immunization (i.e., one week prior to the 2nd immunization) and the second will occur three weeks after the 2nd immunization (i.e., one week prior to the 3rd immunization). The purpose of these conference calls will be to review the accumulated safety data in order to determine whether or not the study should proceed to the next immunization. The study will not proceed to the next immunization unless explicitly agreed to by the members of the Safety Monitoring Committee, either in the form of a letter or email from the Local Medical Monitor. Other conference calls and/or meetings may be required.

The investigator will inform the SMC of:

- All subsequent protocol amendments, informed screening or study consent form changes or revisions of other documents originally submitted for review
- Serious adverse events (SAEs) and grade 3 adverse experiences (as defined in Table 3, section 10.2) occurring during the study, regardless of relationship to the study vaccine
- New information that may affect adversely the safety of the subjects or the conduct of the study.

The SMC will be empowered to put the study on hold pending review of potential safety issues. The SMC would request additional information from the Principal Investigator as needed and will perform any appropriate statistical calculations to support discussions with the DSMB. Final recommendations to permanently terminate or restart the study is made by the DSMB to the sponsors. All documentation provided to members of the SMC for information and review must be treated in a confidential manner.

